8. STATISTICS AND DATA ANALYSIS

8.1 Sample Size

The scores for the primary outcome measure, the QODD, range from 0 to 100. Hales et al 2014 [26] identify 30 and 70 as cut-offs for distinguishing terrible/poor, intermediate and good/almost perfect quality of death. Hence, on the basis of a difference of 10 points representing a meaningful change, and using a standard deviation of 16.41 [27], at least 44 participants in each model type would be required for comparisons between any pair. In order to allow for participant drop out of 33% we propose a sample size of 66 patients per model type (up to 4 models). Our drop out rate is based on a prospective trial of an intervention which followed up with the carers of patients involved who were sent the 24 item QODD questionnaire by post 4-6 months post death. They received a 55.4% response rate and we predict that the contact through bereavement services and phone interview approach we propose will achieve a better response than the postal survey approach used in this study [28].

Based on estimated H@H service size and annual throughput of patients we estimate that recruitment of 66 per model type is achievable for medium and large units in particular. The National Minimum Data Set 2013/14 by the National Council for Palliative Care [29] grouped H@H services by size into roughly 3 equal groups:

- Small fewer than 191 patients per annum
- Medium 191-310 patients per annum
- Large more than 310 patients per annum

However our final range of models and possible case study sites is unknown until interpretation of the phase 1 survey results. If sites are smaller it will be possible to recruit two or more case study sites of the same model type to reach the overall sample size of 66. In the final regression modelling process (outlined below) we would be able to employ a dummy variable to distinguish between the two providers to check for differences.

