3. STUDY DESIGN

Our research design is informed by realist evaluation [16-17] that will be used to identify candidate programme theories that will be tested and refined throughout the proposed research in order to address our objectives. The funded programme of research will be conducted in 3 phases. This protocol outlines the research and processes for Phase 2 and subsequent Phase 3 consensus events (section 8.5).

Phase 1: Survey

A national telephone survey will be conducted of all known H@H services in the Hospice UK service directory to map the range and variation of H@H services in order to develop a typology of models. This phase has received HRA approval (HRA ref # 17/HRA/0299).

Phase 2: Case studies.

To ensure maximum range, we will purposively select up to 8 case studies of H@H services that vary in model 'type' and location (1-2 case studies per model). 66 patients per model type will be recruited and tracked over time (until death) through data collection from the service provider and the patient's

carer. The primary outcome will be the quality of death and will be collected post death. This will be collected using the Quality of Dying and Death (QODD) tool, a validated interview instrument conducted with bereaved carers [18-20]. Secondary outcomes will include holistic patient assessment (iPOS) [21] and assessment of care by bereaved relatives (VOICES) [22] and service use (AHCR) [23]. Regression analysis will be used to isolate the impact of each service model on quantitative outcomes. An embedded economic analysis will capture resource use and calculate costs. Barriers and enablers to service provision will be explored through in depth interviews with carers, commissioners and providers. Analysis will be iterative with the aim of testing and refining programme theories and to develop provisional context-mechanism-outcome (CMO) configurations. Normalisation Process Theory (NPT) [24] will be used to understand why a model has or has not been embedded within a whole system of care.

[figure not shown]
Phase 3: National consensus workshops.

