4. STUDY SITES

The findings from phase 1 were used to create a H@H service model typology comprising 4 model types (see Figure 1). This forms a sampling framework to select case study sites from H@H services in England (ideally from hospices responding to the phase 1 survey). Each type of H@H service within the typology will be represented by one or more case study sites. We also anticipate that the sample will incorporate geographical spread, mixture of deprivation populations and include services that are innovative or more traditionally delivered. Case study sites will be invited by the Chief Investigator to participate.

Figure 1: H@A service model typology

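### The 44 per model type assumes independent patients, but each model is seen at only one or two sites, so the regression cannot isolate a model effect and the stated precision is too favourable

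*Protocol*

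**What the plan says.** Protocol 8.1 sizes the study on the QODD score for pairwise comparison of model types. It works "on the basis of a difference of 10 points representing a meaningful change" and "using a standard deviation of 16.41", and concludes that "at least 44 participants in each model type would be required for comparisons between any pair". Allowing for 33% drop-out, this becomes 66 recruited per model, for up to four models. No ICC or design effect appears.

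On sites, Section 3 plans up to 8 purposively selected case studies, one or two per model. Section 4 says "Each type of H@H service within the typology will be represented by one or more case study sites", so one site per model complies with the plan. Section 8.1 adds further sites of the same model only where sites are too small to supply 66 patients, and not to obtain replication. There it says that "we would be able to employ a dummy variable to distinguish between the two providers to check for differences".

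On analysis, Section 3 says "Regression analysis will be used to isolate the impact of each service model on quantitative outcomes". Section 8.2 describes exploratory regression of QODD on service model type with backward elimination, adjusting for patient sociodemographics, clinical state and carer characteristics. It names no site term.

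**The concern.** The quantity of interest is a difference between service models, but models are delivered by sites and patients are sampled within sites. Patients of one hospice share its staff, its local population and the neighbouring services, so their outcomes are likely to be correlated. The effective information about a model then depends on the number of sites as well as the number of patients.

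With one site per model the model coefficient is exactly the site coefficient. Patient-level covariates cannot separate the model from its location, and no later choice of method can create the missing replication. With two sites per model, site is nested in model. A fixed provider dummy can show that the two sites differ, but it leaves the standard error of the model contrast based on variation between patients only.

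At stake is whether a difference between particular hospices is read as a property of a type of service, with intervals that are too narrow. Section 11 promises guidelines on which models or features work best and at what cost, so the reading matters.

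**Working it through.** **Inputs.** From Protocol 8.1: difference 10 points, SD 16.41, 44 evaluable per model, 33% drop-out. From Section 3: one or two sites per model. Assumed, because the document does not state them: two-sided 5%, 80% power, and ICC 0.01 / 0.02 / 0.05.

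**1. Reproducing the plan's figure.**
- Normal approximation: n = 2 × (1.96 + 0.842)² × (16.41/10)² = 42.3, so 43 per group.
- Two-sample t-test (noncentral t): power is 79.8% at 43 and 80.7% at 44, so 44 per group.
- Drop-out: 44 / 0.67 = 65.7, so 66.
- Alternatives do not fit: one-sided 5% with 80% power needs 34, and two-sided 5% with 90% power needs 57.

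The 44 is therefore an independent-patient two-sample figure with a design effect of 1. Its arithmetic is correct.

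**2. Design effect.** DE = 1 + (m − 1) × ICC, where m is the number of completers per site: 44 with one site per model, 22 with two. Effective n = 44 / DE.

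**3. True error of a nominal 5% pairwise test that ignores site.** 2 × [1 − Φ(1.96 / √DE)].

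| Sites per model | ICC | DE | Effective n | True error |
|---|---|---|---|---|
| 1 | 0.01 | 1.43 | 30.8 | 10.1% |
| 1 | 0.02 | 1.86 | 23.7 | 15.1% |
| 1 | 0.05 | 3.15 | 14.0 | 27.0% |
| 2 | 0.01 | 1.21 | 36.4 | 7.5% |
| 2 | 0.02 | 1.42 | 31.0 | 10.0% |
| 2 | 0.05 | 2.05 | 21.5 | 17.1% |

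With one site per model there are no site-level degrees of freedom, so the data cannot estimate the between-site variance and the error cannot be corrected in analysis.

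**4. Power for 10 points with two sites per model, variance inflation only.** SE = 16.41 × √(2 × DE / 44), which is 3.50 at ICC 0 and 3.85 / 4.17 / 5.01 at the three ICCs. Power = Φ(10 / SE − 1.96) = 74% / 67% / 51%, against about 81% with independent patients.

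**5. Power with a site-level test.** If all four models had two sites, the variation between sites within models would have 4 × (2 − 1) = 4 degrees of freedom. The noncentral t with 4 df and the same SEs gives:

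| ICC | Power for 10 points | Difference detectable with 80% power |
|---|---|---|
| 0 | 58% | 13.2 |
| 0.01 | 51% | 14.5 |
| 0.02 | 45% | 15.7 |
| 0.05 | 34% | 18.8 |

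The first row separates two causes. Going from patient-level to 4 degrees of freedom costs about 23 percentage points (81% to 58%) with no clustering at all. Clustering then takes a further 7 / 13 / 24 points.

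**The case against.** The strongest reply is that the plan does not rest its inference on this regression. Section 8.2 calls the modelling exploratory and speaks of association. Sites are chosen on purpose to give range. Objective 1 in Section 2 covers settings as well as models, and the guidance is shaped by interviews, context-mechanism-outcome configurations and two consensus workshops. Purposively chosen sites are not a random sample of their model, so a random site intercept is itself debatable, and fixed provider terms with inference limited to the studied sites are a recognised alternative. Covariate adjustment could also reduce between-site variance. The exact form of the model may properly be left to a statistical analysis plan.

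Much of this stands. It limits three inferences that a reader might draw:

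- A reader might infer that ignoring clustering cuts power from about 80% to 51% / 45% / 34%. It does not: at ICC 0.01, most of that fall comes from the 4-df test.
- A reader might infer that a chance difference between hospices will be reported as a model effect and turned into national guidance. The documents do not support that certainty. The error rates are raised, not certain, and guidance has other sources.
- A reader might infer that model and site are inseparable throughout. With two sites per model, site is nested in model; full aliasing applies only to a model with one site.

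What does not stand is the defence of the claim itself. An exploratory label in 8.2 does not support the verb *isolate* in Section 3. Inference limited to the studied sites is what the fix asks the protocol to say. A later analysis plan could add a site term, but it could not supply replication or restore the precision stated in 8.1.

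**Conclusion.** The concern holds. The 44 and 66 are computed correctly, but only for independent patients, and the design has one or two sites per model. For a model with one site, the model effect cannot be separated from the site effect, whatever the ICC. For two sites per model, the optional dummy does not bring between-site variation into the model contrast.

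The direction is firm for any ICC above zero; the size is illustrative. Over an assumed ICC of 0.01 to 0.05, the true error of a nominal 5% pairwise test is about 10% to 27% with one site per model and 7.5% to 17% with two. Power for 10 points with two sites is about 74% to 51% from variance inflation alone. The lower site-level figures (58% at ICC 0; 51% to 34% over the range) assume exactly two sites in each of four models, which the plan does not promise. All figures use the unadjusted SD, equal site sizes, and an inferred two-sided 5% level.

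**What to change.** 1. **Section 8.1.** State that 44 per model assumes no between-site variation and an analysis on patient-level degrees of freedom. Give the less favourable power or detectable difference over a range of ICCs.
2. **Section 3.** Replace the claim to isolate each model's impact with wording on association among the studied sites. Report any contrast involving a single-site model as a comparison of sites.
3. **Models with two or more sites.** Report the model contrast with between-site variation reflected in its standard error, for example covariate-adjusted site means shown by site, in place of only an optional dummy check. The exact method can be left to the analysis plan.
4. **Desirable where feasible.** Use two sites for each model within the existing ceiling of 8, about 33 recruited patients per site (66 / 2).

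Items 1 to 3 cost wording and a less favourable stated precision. Item 4 needs no extra patients, but it is not free: each added site brings site-specific assessment, staff training, 5 to 10 provider and commissioner interviews, and service costing. It allows between-site variation to be seen, but does not restore 80% power for 10 points.

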6.2 CARERS

After consent, a member of the research team will contact the carer as soon as possible to collect health service use data retrospectively for up to two months prior to recruitment. This data will be collected using the Ambulatory and Home Care Record (AHCR) that has been customised for use in this study (24). Contact will then be made on a fortnightly basis, by phone to collect prospective health service use data in the same way. This will take approximately 15 minutes every 2 weeks. The carer will be given a diary at the time of consent to be used as an aide memoire for fortnightly data collection telephone calls from the research team. The use of this diary is optional.

Post bereavement

Post-bereavement, a follow up letter will be sent to carers to remind them that the research team will be in touch to collect further data. This letter will include information sheets about the QODD questionnaire and also about the in-depth interview.

Questionnaire

Participants will be given options to do the QODD over the phone, using an online survey tool or by post. The following outcome data will be collected at up to two time-points: immediately post bereavement (optional, carer preference at last health resource data collection telephone contact); at around 1-6 months post bereavement:

- Quality Of Dying and Death (QODD) 7 day recall, Version 1
- 2 short questions about the overall care received

Where 3 attempts to contact the participating carer by telephone have been made with no success, a paper copy of the above follow up measures will be posted to the carer for completion on one occasion only. This will be accompanied by a cover letter to explain that the research team have been unable to contact them and/or if they would prefer to complete the questionnaire at home they can do so.

Optional interview

An in depth interview will be completed by a subset of participants only and will include semi-structured interview questions. We will initially interview approximately 20 per service model type with a stopping criterion of 3 interviews with no new themes coded in order to achieve data saturation (see qualitative data analysis) [25].

If the QODD is collected by telephone, the researcher will ask the participant if they would be willing to participate in an optional in depth interview by telephone or in person to understand more about the H@H service received.

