If the QODD questionnaire is done in the postal or online form, carers can indicate if they would be happy to take part in an optional interview at the end of the questionnaire. If the postal or online QODD questionnaire is not completed within 1-2 months, a final follow up letter will be sent to ask carers to take part in the optional interview only. No further attempts will then be made to contact the carer by telephone unless carers indicate their willingness to take part in an interview in the postal/online QODD questionnaire or final follow up letter reply slip.

All study data will be collected by October 2019. Therefore, patients who are recruited and are still alive after 30 June 2019 will not be included in the study analysis.

[figure not shown]

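### The 33% allowance behind 66 recruits per model has no figure to support it, leaves no slack, and does not count patients still alive at the cut-off

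*Protocol*

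**What the plan says.** Protocol section 8.1 takes 10 QODD points as the difference that matters and a standard deviation of 16.41, and concludes that "at least 44 participants in each model type would be required for comparisons between any pair". It then adds the attrition allowance, to "allow for participant drop out of 33% we propose a sample size of 66 patients per model type". The rate is attributed to an earlier study that posted the QODD to carers four to six months after the death: "They received a 55.4% response rate". The protocol predicts a better result here, for two reasons: contact through bereavement services, and interviewing by telephone.

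Section 6.2 sets the follow-up rules.
- **Mode:** "Participants will be given options to do the QODD over the phone, using an online survey tool or by post". After three failed calls, one paper copy is posted, once.
- **Last contact:** if a postal or online QODD has not come back within one to two months, "a final follow up letter will be sent to ask carers to take part in the optional interview only". Telephone contact then ends unless the carer agrees to be interviewed.
- **Cut-off:** "patients who are recruited and are still alive after 30 June 2019 will not be included in the study analysis".

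Appendix 1 (Distress Protocol) says that data are collected only face to face or by telephone.

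**The concern.** Four features of the plan bear on whether 66 recruits yield 44 completed primary outcomes.

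1. The source cited for 33% lost 44.6% (100 − 55.4). No figure supports the step from 55.4% to 67% response.
2. One of the two reasons given for that step, the telephone approach, describes only one of the three modes that 6.2 offers. Appendix 1 gives yet another account. The three sections do not describe the same procedure.
3. The allowance is derived from a response rate among carers after a death. A patient alive at the cut-off drops out before any carer can be asked for a QODD, so this loss comes on top. Section 8.1 does not mention it, and no replacement rule is described.
4. The last letter to a carer who has not returned the form asks for qualitative data and not for the primary outcome.

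At stake are the expected number of primary outcomes per model, the power for each pairwise comparison, and some QODD forms that are not requested again.

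**Working it through.** **Inputs.** From section 8.1: difference 10, SD 16.41, 44 needed, 66 recruited, drop-out 33%, cited response 55.4%. Alpha and power are not stated there. Assumed: 5% two-sided and 80% power, equal groups, two-sample t-test.

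**The plan's own figures.**
- Normal approximation: n = 2(1.96 + 0.8416)² × 16.41² / 10² = 42.3, so 43 per group. The t-test solution is 43.25, so 44. Under the normal approximation, one-sided 5% with 80% power gives 34, and two-sided 5% with 90% gives 57. The assumed pair is therefore the reading that fits.
- Inflation: 44 / (1 − 0.33) = 65.7, so 66. Both figures reproduce.
- Power at 44 per group is 80.7%.

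**Slack.** 66 × 0.67 = 44.2. The plan needs 44/66 = 66.7% of recruits to complete and assumes 67%. A single survivor among 66 gives 65 × 0.67 = 43.6, already below 44.

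**Two losses.** With s the share alive at the cut-off and r the carer response among the rest:

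completers = 66 × (1 − s) × r

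The protocol gives neither recruitment dates nor survival beyond two months, so s is an assumption, shown from 5% to 15%. Section 8.4 reports that 38% of patients in the team's earlier study were referred more than two months before death, so s is unlikely to be zero.

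| s | r | Completers | Power for 10 points | Detectable difference at 80% power | Response needed for 44 |
|---|---|---|---|---|---|
| 0 | 67% | 44.2 | 81% | 9.9 | 67% |
| 5% | 67% | 42.0 | 79% | 10.2 | 70% |
| 10% | 67% | 39.8 | 77% | 10.4 | 74% |
| 15% | 67% | 37.6 | 74% | 10.7 | 78% |
| 0 | 55.4% | 36.6 | 73% | 10.9 | 67% |

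The last column is 44 / (66 × (1 − s)). For example, at s = 10%, 44/59.4 = 74%.

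**Collection modes side by side.** Section 8.1 argues from telephone interviews as against post. Section 6.2 offers telephone, online or post at the carer's choice, with one posted copy as a fallback. Appendix 1 allows only face-to-face or telephone collection. Post and online completion in 6.2 cannot be squared with Appendix 1, and the argument in 8.1 covers only part of what 6.2 allows.

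**The case against.** The strongest reply is that 8.1 contains no error. The division is right, the 55.4% is disclosed, and the protocol openly argues that it will do better. That argument has substance. Unlike the carers in a postal survey months after a death, these carers consent at entry, give their preferred number and time, are telephoned every fortnight and receive an advance letter after bereavement. They may complete the QODD at up to two time-points and are called three times before the single posted copy. Contact through bereavement services is a second stated reason, independent of mode. Telephone remains available, and adding post and online may raise response as readily as lower it.

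All of this stands, and it rules out some stronger readings. A reader might infer that the sample-size arithmetic is wrong; it is not. A reader might infer that the design will deliver only 55.4%; the documents do not say so, and that rate comes from a postal-only design. A reader might also multiply 55.4% by a survivor loss: 66 × 0.85 × 0.554 = 31.1 completers, about 66% power. That stacks two unfavourable assumptions, one of which cannot be derived from the protocol, and it should not be presented as the study's power.

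The final letter can be defended as restraint towards bereaved people, a concern evident in Appendix 1. But the letter is sent anyway and already contains a request.

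The reply does not supply a figure for 67%, a place in 8.1 for survivors, or any slack to absorb them. These are protocol matters: an analysis plan cannot recover a form that was not requested again.

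**Conclusion.** The point holds as an unsupported and incomplete allowance, not as a miscalculation. The 67% response is a planning judgement without a supporting figure, and its stated rationale matches only part of the collection procedure. The exclusion of survivors is a real and separate loss; with a margin of 0.2 of a completer, a single survivor per model takes the expected number below 44.

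The likely effect is moderate. At 67% response and 5% to 15% survivors, about 42 to 38 carers complete per model, with 79% to 74% power and a detectable difference of 10.2 to 10.7 points. The cited 55.4% with no survivors gives 36.6, 73% and 10.9 points, and serves as a pessimistic bound. These figures rest on 5% two-sided testing and 80% target power, both inferred, and on an assumed survivor share. The direction of the effect does not depend on the size of that share.

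**What to change.** 1. **Section 8.1.** Keep 66 recruits per model, but state the expected completers as the product of two losses: the sponsor's own estimate of the share alive at the cut-off, based on its recruitment calendar, and carer non-response shown from 33% to 45%. Give the resulting completers, power and detectable difference, and state alpha and target power.
2. **Sections 6.2, 8.1 and Appendix 1.** Reconcile the account of how the QODD is collected, and base the response argument on the mixed modes actually offered.
3. **Section 6.2.** Let the final follow-up letter enclose the QODD again, with an optional offer of telephone completion, alongside the interview invitation.

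The cost is a less favourable stated figure, a minor amendment, and one further optional request to bereaved carers in a letter that is already sent. How much response the extra enclosure would gain is not known.
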